Resources: Facilities and equipment and key personnel roles. The majority of project personnel will be located at Center for Clinical Management and Research (CCMR; Drs. [name], [name], [name]) where office space and equipment for them will be provided. The ED at the VAAAHS will provide space for peer mentors and research supervisor, with a telephone, to conduct the research assessments and to conduct the brief personalized advice protocol. Key roles are described in the budget justification. Project staff in Ann Arbor will have weekly meetings to ensure that the study is progressing well. In addition, study staff will have a 2-hour meeting once a month to discuss logistical and larger scientific issues.

Data management and safety. [name] will be responsible for the safety and security of patient-level data, stored on firewall-protected servers at CCMR. A Master's-level data manager within CCMR will conduct the initial double data entry, cleaning, linkage and analysis. The project will create a shared study folder accessed by study personnel. Once the final file is completed in year four, in accordance with current regulations articulated by the 1996 Health Insurance Portability and Accountability Act (HIPAA) Privacy Rule, private health information will be stripped with the exception of ages and dates and kept physically separate on the VA secure network with password protection.

HUMAN SUBJECTS

Risks to Human Subjects

Human Subjects Involvement and Characteristics. Data will be collected from Veterans, men and women, ages 18 years and older, recruited from the VA Ann Arbor Healthcare System (VAAAHS) Emergency Department (ED). Screening will last through the end of month 12, year 3 (30 months). Follow-up assessments will begin at the start of month 10 in year 1 and continue until the end of month 12, year 4. Key informant qualitative interviews will occur in the first 9 months of year 4. Data entry, cleaning and/or analysis will begin at the start of month 7 in year 1 and continue through the end of year 4. Dissemination of findings and report writing will begin with analyses of the screening data around month 10 of year one and continue through the end of the project.

We expect that 15% of the screened patients will have a positive screen and will be randomized, yielding 225 per group (total=450). Based on data from the study site, we anticipate the gender composition of the sample to be approximately 7.5% female and 92.5% male; we expect the following racial composition of the sample: approximately 20% African American, 75% Caucasian, and 5% other (i.e., Asian, American Indian, Native Hawaiian or Other Pacific Islander). We also expect that 1-2% of adults will identify as Hispanic ethnicity.

Inclusion criteria for screening. 1) adult Veterans age 18 years of age or older presenting for care in the VAAAHS ED; 2) medically stable and able to provide informed consent.

Inclusion criteria for the RCT. Individuals will be eligible to participate in the RCT if they: (1) have an AUDIT-C score of 4 or more for men and 3 or more for women in the prior 3 months, indicating that they meet criteria for hazardous use (NIAAA 2005; World Health Organization); 2) a telephone and/or the ability to provide information about individuals who can help contact the participant. Importantly, the study will include those with more severe problems to address the problems and needs of Veterans who can most benefit from linkage to primary and secondary care. The more severe users will receive content that actively encourages treatment initiation.

Exclusion criteria for screening. (1) patients who do not understand English; (2) prisoners; (3) current or recent substance use treatment in past 3 months; (4) patients currently in or having received peer services in the past 3-months per medical record; (5) pregnant women; (6) patients deemed unable to provide informed consent as stated above; and (7) profound psychotic symptoms and/or cognitive deficits that would prevent patients from understanding the content of the intervention and/or assessments.

It has been our experience that some patients are unable to provide informed consent on entry to the ED (e.g. psychotic symptoms; acute intoxication) but that their status will improve sufficiently prior to ED discharge to make them eligible to be approached by research staff. Participants may be excluded at the discretion of the Principal Investigator based on participant or study staff best interest (e.g., if participant should become physically or verbally aggressive towards study staff, or if the study staff know a patient or their family

personally, in order to fully ensure participant privacy).

Exclusion Criteria for RCT. (1) individuals currently active in or having recently completed alcohol or other substance abuse treatment in the past 3 months; (2) patients currently in or having received peer services in the past 3-months per self-report screening.

After providing written informed consent to participate in the RCT component of the study, completing the baseline assessment, eligible participants will be randomized into Alcohol Peer-Mentored (APM) Intervention condition or the Brief Advice (BA) condition. Participants in both conditions will receive brief personalized feedback advice from an ED clinician or the peer mentor. For those in the APM condition, following the brief advice session, the peer will set up the first post-ED contact with the participant. All participants in both conditions will receive a community and VA resource guide covering health care and community assistance options.

All participants who choose to participate in the study will complete a baseline assessment and three additional follow-up assessments (i.e., 3-, 6-, 12-months post baseline).

Sources of Research Material. Data will be obtained by means of interviews and self-report inventories specifically for research purposes. Primary sources of data for this study will be gathered from an initial eligibility screening assessment, baseline assessment, and follow-up assessments (i.e., 3, 6, and 12 months post baseline). To supplement self-report measures, we will abstract VA records for health services information such primary care visits, substance abuse treatment, outpatient mental health service utilization.

Potential Risks. There is a minor potential risk for breaches of confidentiality with assessment data. The risk of a violation of confidentiality exists because human participants will be disclosing personal information, both in assessments and intervention sessions. This risk is related to the damage that could be caused by an inadvertent release of sensitive information (e.g., psychiatric symptoms, substance use, etc.). Our research team has considerable experience in maintaining the confidentiality of study datasets and will have procedures in place to ensure data confidentiality. (See details of protections below) All investigators have completed training in the requirements for handling protected health information as outlined by the Health Insurance Portability and Accountability Act (HIPAA). Participants will be informed of the procedures taken to protect their confidentiality. The focus of this study is not on child abuse or intention to harm others. However, because of the nature of the study (hazardous drinking and/or dependence) these issues may arise. The consent form will contain a statement explaining mandatory reporting requirements for information regarding child abuse and intention to harm self or others prior to participating in the study.

There is also a slight risk of psychological discomfort to study participants as a result of being asked personal questions, particularly during the assessments. Participants may also become anxious or upset during discussions about hazardous drinking that occur during the ED-based RA or peer delivered brief advice session and during the continuing peer mentoring intervention. Study staff will be trained to respond to this emotional distress and to refer participants to appropriate resources as necessary. All participants will be free to terminate the assessments at any time or refuse to respond to any questionnaire item.

There is a small risk that the intervention might upset participants. The project will utilize a standardized intervention content, with includes motivational, supportive, nonjudgmental language targeting behavior changes. The peer interactions are designed to be collaborative and avoid the use of any statements that could be perceived as coercive by participants. It has been the experience of the project's investigators that these approaches dramatically diminish risks to participants from the study's intervention. Still, unexpected events are always possible in intervention research. The investigators of this project will establish protocols for study staff to guide them in responding to crisis or potentially harmful situations.

Adequacy of Protection against Risks

Recruitment and Informed Consent. All eligible patients will be approached (after verifying record that the patient is sufficiently stable) by the research staff and recruited for the screening portion of the study. Those interested in participating in the study will complete a Mini-Cog standardized assessment to screen for cognitive impairment. If appropriate to move forward, they will be informed of the general nature of the survey and study, what their involvement entails, the risk/benefits, and limitations to confidentiality. As part of the informed consent process, patients will be able to describe to the research staff the essential elements of the study for which they are providing consent. Patients who are notably sedated or confused at the time of screening will be re-approached later in their ED stay if they are still interested. The study team has found that this protocol has worked well for recruitment in other ED-based alcohol studies. All participants will be told that participation is voluntary, that they can withdraw at any time, and that this will not impact their VHA care. The limits of the NIH Certificate of Confidentiality will be explained in the written consent form, but study staff will

also verbally explain the limits of confidentiality. When providing written informed consent, participants will be given a copy of the consent form and the original will be filed in a confidential research file.

Protections Against Risk. Several steps will be taken to minimize the risk of breaches of confidentiality. First, every effort will be made to ensure that study data are always confidential, in terms of staff training and data storage, so that data forms cannot be linked to a particular person except through the study cross-walk file that is securely stored and password protected inside the VA network. Training of staff will include information about the importance of confidentiality and techniques to maintain confidentiality of all information reported by research participants.

Risks will be discussed with individuals choosing to participate as part of the informed consent process. Throughout the study, VA IRB and HIPAA guidelines will be followed to ensure privacy of patient data. Unique identification numbers will be assigned to all participants who complete the assessments. The participant code will appear on assessment forms. All data forms and assessments will be coded with this number, rather than with a name. Participants' names and other identifying information will be kept separately from study data on password-protected files on a secure server with restricted access and/or in a locked cabinet in a locked room; and only participants' unique ID number will be kept in the database on password protected file. All research data will be presented in aggregate form only. Additionally, we will apply for a Certificate of Confidentiality from the NIH to protect the confidentiality of our participants.

Because there is a small risk that participants may experience some distress or psychological discomfort when answering assessment questions, participants will be made aware of their right to refuse to answer any questions that make them uncomfortable or that they do not wish to answer, and they will be informed of their right to withdraw from the study at any time without penalty. Participants may also be informed that they can take breaks. Additionally, study staff will be trained extensively to respond to emotional distress and to discuss concerns and issues should they arise. More specifically, study staff will be trained to perform attentive and empathic listening. To minimize this risk, research staff will be available during and following participation in the intervention condition and during assessments to manage (i.e., discuss and refer as needed) any unexpected issues that may arise. It has been the experience of the project's investigators that these approaches dramatically diminish risks to participants from the study's intervention.

It is possible that some participants will report levels of suicidal thoughts and plans that will require further intervention. We will have a detailed suicide risk assessment protocol and, if research staff determines that a participant is at acute suicide risk, we may ultimately need to inform treatment staff at the VA. Research staff, in consultation with Drs. [name] or [name] will evaluate if the participant is at acute risk of suicide based on the presence of a coherent plan and a desire to act. For individuals that trigger the need for a suicide assessment, the study coordinator will inquire about plan, severity, and risk factors. Drs. [name] or [name] will be contacted for individuals that are at high risk (i.e. distinct and/or immediate plan to harm oneself). The study physician will make a decision about appropriate next steps, including the need for emergency or follow-up evaluation, requesting the participant to contact a family member or friend, contacting facility/hospital staff member (i.e., psychiatrist on call, participant's provider) before the study staff leaves the location, performing a warm handoff.

Potential Benefits of the Proposed Research to Human Subjects and Others

It is believed that research participants may be helped in a number of ways. All participants will be assessed for alcohol use, progress toward cutting down/stopping and seeking primary or specialty care, as needed. Participants randomized to the APM condition will receive a single-session intervention in the ED aimed at addressing perceived barriers and facilitators cutting down/stopping alcohol use and seeking primary or specialty care. They will also work with the peer to set up the first at least 6 contacts over the next 2-month period to facilitate care seeking and changes in alcohol use. All participants will receive written materials that include VA and community resources encouraging them to seek primary and specialty care, if needed. Others may also benefit from this research. If efficacious, implementing a brief and effective peer-delivered alcohol intervention with ongoing structured peer mentorship can be rolled out nationally in the VHA and can have a significant and substantial impact on alcohol use and consequences. This study has the potential to enhance service delivery to Veterans experiencing alcohol problems, and to assist with coping during a potential crisis in the future, while posing few physical risks beyond those associated with usual care. In sum, the potential benefits for the research far outweigh the risks to participants.

Importance of Knowledge to Be Gained

Reducing alcohol problems is an urgent imperative within the Department of Veterans Affairs. There is a clear need to link individuals with more serious alcohol problems to available VA resources that can improve their mental and physical health outcomes. Despite significant investment in alcohol screening and

brief interventions in the VHA, many high-risk Veterans are not utilizing needed services and/or changing alcohol use patterns. This study is one of the first attempts to directly test the effect of peer-delivered alcohol interventions with post-ED peer mentorship to link with and engage in VA primary and specialty care. More so, this RCT will evaluate the feasibility and effectiveness of a low-cost and easy-to-deliver intervention designed to encourage the use resources. Developing this peer mentorship intervention has the potential to have a significant and substantial impact on the Veterans with more serious alcohol problems treated in the VHA and could be modified and exported to other populations and settings.

Inclusion of Women and Minorities

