It is important to explore the mechanisms of action that explain how the APM intervention influences change. The **secondary specific aim is to determine the mediators** (e.g., motivation to change, self-efficacy, coping, perceived helpfulness of social support) of the effect of the intervention and linkage on subsequent alcohol use and alcohol-related consequences. An **exploratory aim is to conduct structured qualitative interviews** in order to understand barriers and facilitators of implementation of the APM

intervention in the ED with Veteran participants, clinicians, and peer mentors.

RESEARCH PLAN

Background

Extent of Hazardous and Harmful Drinking in Veterans. The recent Institute of Medicine (IOM) report highlights alcohol as a key problem needing intervention and/or treatment among military personnel, in general, and Veterans, in particular. Hazardous drinking occurs along a spectrum of severity from occasional over-consumption at levels that could be damaging to one's health, to engaging in risky behaviors (e.g., driving). Harmful drinking includes the development of an alcohol use disorder (AUD), which is characterized by a series of alcohol-related problems. Harmful and hazardous drinking, including binge drinking,¹¹ and alcohol-

Drinking Definitions

- **Harmful drinking:** Use of alcohol that causes complications (includes abuse and dependence, problem drinking)
- **Hazardous drinking:** Use of alcohol that increases risk for complications (includes risky or at-risk drinking)
- **Non-hazardous drinking:** Use of alcohol without clear risk of complications (includes beneficial use)

Source: World Health Organization

related problems are particularly common among Veterans.^{5,12-15} The VHA serves a high proportion of Veterans with alcohol and comorbid mental health problems.^{12,13,16} The percentage of Veterans enrolling in VHA with mental health problems, including substance abuse, has dramatically increased with the influx of Veterans from Operation Iraqi Freedom/Operation Enduring Freedom (OIF/OEF). Official VHA data for the first half-million of these Veterans seeking care in VHA documented that 56% presented with a mental health problem, including substance abuse. This is a dramatic increase from Veterans in earlier wars. Hazardous and harmful drinking (AUDs) are common

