Data Management. The project's data manager will conduct all data management and analysis activities under the supervision of Drs. [name] and [name]. Research staff will use double entry procedures and reconcile discrepancies. Data cleaning will be conducted throughout data collection to ensure a quality final dataset for analysis. Statistical Analysis System (SAS) will be used to examine and prepare data for the analysis.

General analytic approach. Hypotheses will be planned a priori, and will be limited to the examination of a limited number of outcomes. We will utilize an "intent-to-treat" approach. All analyses will use two-sided tests because it is possible that the APM participants might have worse outcomes compared to CBA participants. Analyses will begin with descriptive data analyses to determine distributions of key variables, to collapse categories, if necessary, and to review data for outliers and clear anomalies. Tests for linearity, independence, missingness, and distributional assumptions will also be performed. Normalizing transformations of the dependent variables will be utilized, if necessary. We will validate the randomization scheme by comparing the initial groups on key variables that could be associated with the outcomes. Where we identify significant differences between groups, we will adjust for these variables, as well as other addictions treatment received if it was not initiated by referral from the APM or CBA clinician (and thus a potential mediator of effect). Prior to fitting any analytic models, a graphical exploration of the outcome variables will be conducted to select the appropriate models based on variable distributions.

Missing data. Every effort will be made to minimize missing data. Where we have missing covariates that are necessary for analysis, we will perform multiple imputation of missing data and combine the results from 5 imputations based on Rubin's method to produce an estimate and the corresponding confidence interval accounting for missing data uncertainty.⁸⁸ For follow-up attrition, the proposed mixed-effects regression model will allow the use of data from all participants (not just those with complete follow-up) and provide unbiased

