Data Analysis for Aim 2: The focus of Aim 2 is to study intervention effects on secondary outcome of frequency of primary care and mental health specialty care visits (as two separate outcomes) from the TSR, calculated as an average number of visits per month during each follow-up period. Similar to Aim 1, analyses will generally use a mixed effect model framework. As described above, initial analyses will examine the distribution of outcome measures over follow-up in order to select an appropriate model (e.g. Poisson regression or a related method for counts of visits). Our analysis strategy will parallel Aim 1 in terms of the independent variables, *random effect for peer/brief advice, focus on time-average treatment effects, and additional modeling of interactions of group and time.*

Secondary Aim will determine the mediators (e.g., motivation to change, self-efficacy, coping, social support) of the effect of the intervention and linkage on subsequent alcohol use and alcohol-related consequences. **Hypothesis:** The effect of randomization to APM compared to BA on the primary outcomes (i.e., alcohol consumption and consequences) will be mediated by differences between groups in motivation to change, self-efficacy, and perceived helpfulness of peer support.

Data Analysis for Secondary Aim: *In order to establish temporal ordering, we will examine whether level of the hypothesized mediators at 3 and 6 months post-baseline mediates the effect of random assignment on 6- and 12-month measures of the three primary outcomes of alcohol use behaviors.^{90,91} We will first determine the whether study condition is associated with the hypothesized mediators over the first six months of follow-up and check for a direct effect of the mediators at 3 and 6 months on alcohol use as measured at 6- and 12-months follow-up. We will estimate the indirect effect of the intervention on alcohol use through the mediators and conduct significance testing of this effect using macros created by Preacher and Hayes.⁹²*

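### The mediation analysis has no linkage term and no consequences outcome, although the secondary aim names both

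*Combined protocol and SAP*

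**What the plan says.** The secondary aim appears in Specific Aims and again under Data analyses. Both places cover mediators "of the effect of the intervention and linkage on subsequent alcohol use and alcohol-related consequences". In Specific Aims the mediators are given as examples: "e.g., motivation to change, self-efficacy, coping, perceived helpfulness of social support".

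The hypothesis under Data analyses concerns the effect of APM against BA "on the primary outcomes (i.e., alcohol consumption and consequences"), which "will be mediated by differences between groups in motivation to change, self-efficacy, and perceived helpfulness of peer support".

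Data Analysis for Secondary Aim asks whether the 3- and 6-month mediators' level "mediates the effect of random assignment on 6- and 12-month measures of the three primary outcomes of alcohol use behaviors". It then states: "We will estimate the indirect effect of the intervention on alcohol use through the mediators".

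Linkage appears in three other places:
- **Data Analysis for Aim 2** takes the frequency of primary care visits and of mental health specialty visits as two outcomes compared by arm.
- **General analytic approach** adjusts for other addictions treatment only "if it was not initiated by referral from the APM or CBA clinician (and thus a potential mediator of effect").
- **Guiding Conceptual Framework** has peer effects running through patient beliefs and self-efficacy. It places linking to care beside cutting down as the resulting behaviours.

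Table 2 schedules the SIP and the service-use measure (TSR/CPRS) at baseline and at 3, 6 and 12 months.

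**The concern.** The aim, the hypothesis and the analysis narrow step by step. The aim has linkage and consequences, the hypothesis keeps consequences, and the analysis has neither. If the analysis is run as written, the trial could find less drinking under APM without being able to say whether entry into care had any part in it. It would also report no indirect effect on consequences. Adding either analysis after the results are known would be post hoc.

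There is a second, conditional worry. Someone who enters care by month 3 may report higher self-efficacy at month 6 and drink less at month 12. If linkage is left out of the model, its effect on drinking can then appear as mediation by self-efficacy or motivation.

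**Working it through.** **1. Comparison of the text**

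| Element | Aim | Hypothesis | Analysis |
|---|---|---|---|
| Cause | intervention and linkage | randomised arm | randomised arm |
| Mediators | motivation, self-efficacy, coping, social support (examples) | motivation, self-efficacy, helpfulness of peer support | the hypothesised mediators at 3 and 6 months |
| Outcomes | alcohol use and consequences | consumption and consequences | three alcohol-use outcomes at 6 and 12 months |

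Linkage drops out between aim and hypothesis, and consequences between hypothesis and analysis. The hypothesis also calls consequences a primary outcome, whereas Table 2 lists the SIP as secondary. Aim 2 supplies the step from arm to service use. No analysis supplies the step from linkage to drinking.

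**2. The plan's own figure**

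The plan states no power for mediation. Its stated 80% power for d = 0.30 with 360 retained reproduces: at 180 per arm and two-sided alpha 0.05, power is 81%. That figure concerns the arm comparison and is background here.

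**3. Size of the misattribution risk (illustrative)**

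Inputs from the documents: n = 360 (Power and Sample Size Calculations), and an odds ratio of 1.79 for treatment assessment (Preliminary Studies). Everything else is assumed.

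- Linkage under BA is 15% or 30%. Under APM the odds are 0.15/0.85 × 1.79 = 0.316, giving 24%; or 0.30/0.70 × 1.79 = 0.767, giving 43%.
- Self-efficacy = 0.3 × arm + e × linkage + noise.
- Drinking = −e × linkage + noise, so self-efficacy has no effect on drinking.
- Self-efficacy is declared a mediator when both arm to self-efficacy and self-efficacy to drinking (given arm) are significant.

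| Linkage effect e | False mediation, linkage omitted | With linkage in the model |
|---|---|---|
| 0.3 SD | about 4% to 7% | about nominal |
| 0.5 SD | roughly 8% to 17% | 3% to 5% |
| 0.8 SD | roughly 35% to 65% | 3% to 5% |

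Ranges span the two base rates and repeated runs. In the same settings, testing linkage as a mediator has about 53% to 76% power at 0.5 to 0.8 SD, and 31% to 56% at 0.3 SD.

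The total effect of APM on drinking implied by these settings is small. It is e times the linkage difference: 0.5 × 0.09 = 0.045 SD at the low end and 0.8 × 0.134 = 0.107 SD at the high end, against the plan's detectable 0.30.

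**4. A second model**

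Here linkage is continuous. The assumed paths are arm to linkage 0.3 SD, arm to self-efficacy 0.3 SD, linkage to drinking −0.4 SD and self-efficacy to drinking zero. The residual correlation r between linkage and self-efficacy is varied. With linkage omitted, the share of the total effect credited to self-efficacy is 0.3 × (−0.4 × r) / (0.3 × −0.4) = r. At r = 0, 0.2, 0.3 and 0.5, false mediation is declared in 4%, 24%, 46% and 78% of trials. With linkage in the model the rate is about 4% throughout. At r = 0 there is no misattribution.

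**The case against.** A reader might infer that the pathway on which the intervention is built goes untested. The documents do not support this. The conceptual framework makes beliefs and self-efficacy the mediating pathway, and the plan does test self-efficacy and motivation. Linkage is an end behaviour there and an outcome in Aim 2, so its response to the intervention is examined.

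A reader might also take the phrase "and thus a potential mediator of effect" as a promise to test referred treatment as a mediator. It only explains why such treatment is left out of the covariate adjustment. The same sentence shows that treatment entry is not wholly absent from the drinking models, since treatment not referred by the study may be a covariate.

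The aim's wording places linkage beside the intervention as a cause, so making it a mediator is one reading among several.

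The simulation assumes that linkage precedes self-efficacy. The conceptual framework points the other way: self-efficacy leads to linking. In that order, conditioning on linkage removes a real part of the self-efficacy effect. The odds ratio of 1.79 also comes from in-person case management for substance use disorders. The same source gives 1.48 for engagement, and this trial also enrols less severe drinkers.

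All of this stands. It rules out the stronger claim, and it rules out conditioning on linkage as the only analysis. It does not remove the mismatch between aim, hypothesis and analysis.

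**Conclusion.** The concern holds as a gap between the stated aim and the specified analysis. Linkage to drinking, and any indirect effect on consequences, go untested although the measures are collected at the needed visits. This conclusion rests on the text alone.

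The risk of crediting a linkage effect to self-efficacy is real but conditional. It runs from about the nominal rate at 0.3 SD to a majority of trials in the most extreme setting. It depends on path values that the documents do not give, and on linkage and self-efficacy being correlated within arm. The rates are illustrations and do not predict what this trial will show.

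The aim is secondary and mechanistic. The Aim 1 and Aim 2 effect estimates are not affected.

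**What to change.** 1. Run the planned mediation analysis also with the SIP at 6 and 12 months as outcome.
2. State the role of linkage (cause, mediator or outcome) consistently in Specific Aims, the conceptual framework, General analytic approach and the secondary-aim analysis. Add linkage as a mediator of later TLFB outcomes, defined as care contact by month 3 and by month 6 from the TSR or VHA records, excluding study peer sessions. Keep this to the mediation models and out of the Aim 1 efficacy model.
3. Report the self-efficacy, motivation and support indirect effects both without and with linkage in the model. Say that linkage may come before them, so that omitting it can inflate their effect, or after them, so that conditioning on it removes part of their effect.

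The cost is SAP wording and a few extra models, with no new data collection. Linkage is not randomised, so its indirect effect relies on there being no unmeasured confounding and should be labelled accordingly.
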